4.5 Patient Replacement

Patients dropping out (i.e., prematurely discontinuing Study Drug treatment) for reasons unrelated to safety may be replaced at the Sponsor’s discretion.

4.6 Study Completion

Primary study completion is defined as the completion of the Week 24 visit, even if one or more interim visits or procedures was/were missed.

Completion of the Extended Follow-Up is defined by the completion of the Week 35 visit even if one or more interim visits or procedures was/were missed.

5 ENROLLMENT AND STUDY PROCEDURES

5.1 Patient Identification Numbers

After signing the Short ICF, patients should be registered into the electronic data capture system to obtain a patient identification number for the study.

5.2 Screening Visit Procedures (Up to 2 weeks, Days -28 to -15) – Initial Screening

Screening will be conducted in a stepwise manner.

The Initial Screening procedures will be conducted under a Short ICF that will include a medical chart review (e.g., medical history, concomitant medication, laboratory data) for eligibility criteria that can be ascertained in this manner (**Step 1**). In addition, the Short ICF will include consent for adjusting or washing out medications as needed. Upon determining eligibility based on medical chart review, Central Laboratory tests including genotyping and Screening IL-6 tests should be submitted to the Central Laboratory (see [Appendix A](#)) (**Step 2**).

During Initial Screening period, patients should be monitored for prospective eligibility based on parameters to be assessed during Full Screening. Specifically, ERI, hemoglobin stability, and stability of ESA and iron dosing should be observed per the Schedule of Events and patients who in the judgment of the Investigator are likely to clear these inclusion criteria during Full Screening should be allowed to enter the 2-week Full Screening period.

Patients who are eligible following Initial Screening should proceed as soon as feasible into the full Screening Period, to ensure that the time from the first Screening IL-6 measurement and randomization does not exceed 6 weeks.

Tentatively schedule the Cardiac MRI to occur during Full Screening.

5.3 Screening Visit Procedures (Days -14 to -1) – Full Screening

Prior to conducting any procedures, informed consent for the full study should be obtained and the Long ICF signed. The Long ICF includes consent for all study procedures subsequent to the Initial Screening.

Every effort should be made to obtain the blood tests for each visit on the same day of the week (e.g. on Wednesdays).

Important: Please note that ESA, IV iron, and dialysate iron dosing should be monitored carefully during this period as it is required to be stable (as defined in the inclusion criteria #8 and #9, [Section 4](#)) in order for patients to be eligible. Update standing orders for these medications as needed.

The following sections summarize the procedures for Week -2 and Week -1. Please see [Appendix A](#) for full details.

Week -2

- Dispense 3 fecal occult blood tests collection materials and review instructions for stool collection with the patient to avoid false positives (see Laboratory Manual for instructions). Request return of the samples within 1 week to allow sufficient time for analyses of these at the Central Laboratory. If necessary, stool occult blood testing may be performed locally if materials have not been returned in a timely manner.

Week -2 and Week -1

- On each of these weeks, obtain, before and after a single dialysis session: pre-dialysis and post-dialysis Central Laboratory tests, pre-dialysis and post-dialysis vital signs and weights, and record the net ultrafiltration (i.e. fluid removed minus fluid administered during dialysis) from the same dialysis session around which above procedures were performed.
 - At any time during these 2 weeks, perform a limited physical examination (see [Section 10.2.3](#)), obtain a 12-lead ECG (see [Section 10.2.2](#)), measure the handgrip strength, and have the patient complete the FACIT-F questionnaire.
 - Instructions for performing the handgrip strength and the FACIT-F questionnaire can be found in the Study Reference Manual
- Collect all 3 stool occult blood tests from patients and submit to the Central Laboratory. Locally performed stool testing may be substituted, if Central Laboratory results are not available prior to randomization.
- Record adverse events and any medication changes.
- Ascertain that the patient remains eligible before proceeding to the next visit
- Schedule the Day 1 visit to occur on a Monday, Tuesday, Thursday or Friday whenever possible.
- Obtain a non-contrast cardiac MRI (see MRI Technical Manual for instructions) in Week -1 or Week -2

5.3.1 Laboratory Re-Testing and Re-Screening

An individual laboratory value may be repeated once during Initial Screening or Full Screening for any reason (e.g., Investigator believes value to be erroneous). Any additional laboratory re-testing must be approved by the Medical Monitor.

Patients failing Screening may be allowed to re-enter Screening under some circumstances with approval from the Medical Monitor.

Patients who are re-screening may follow an abbreviated/modified set of Screening procedures as follows:

- Genotype testing: not required
- Cardiac MRI: not required if previously performed within 12 weeks prior to the re-screening Week -2 Visit date
- Initial Screening medical history: not required. Please note that confirmation of eligibility remains a procedure during Full Screening.
- TB testing: not required if previously performed within 12 weeks prior to the re-screening Week -2 Visit date
- Stool occult blood testing: not required if previously performed within 12 weeks prior to the re-screening Week -2 Visit date
- Short ICF and Long ICF: Re-sign prior to starting re-screening procedures

The following sections summarize the procedures for the Treatment Period. Please see [Appendix A](#) for full details.

5.4 Treatment Period (Study Weeks 1 - 12)

Important: Please note that ESA and IV and dialysate iron dosing should be controlled carefully during this period as they are required to be stable (as defined in [Appendix C](#)). Ensure processes and staff training are in place to avoid inadvertent changes in these medication.

Study Visits during which Study Drug infusions are required should be planned for the same day of the week so that Study Drug administration can occur on a schedule of every 7 days. See [Section 6.1.1](#) for guidance on missed doses.

5.4.1 Week 1, Day 1 (First Dose)

- Randomize the patient
 - Randomization may be performed on Day -1, if needed. Administration of the first dose of Study Drug will continue to define Study Day 1.
- Prepare the Study Drug prior to the anticipated time of administration (see [Section 6.1.1](#) and Pharmacy Manual)
- Perform the hand grip strength prior to the start of dialysis (see instructions in the Study Reference Manual)
- Obtain Central Laboratory blood samples within 15 minutes prior to the start of dialysis
- Obtain a Local Laboratory (or point of care) INR (only for patients on warfarin)
- Obtain an ECG prior to the start of dialysis (see [Section 11.4.5.4](#))

- Have patient complete the FACIT-F questionnaire (see instructions in Study Reference Manual) prior to dialysis or during the first hour of dialysis
- Any time prior to the last one hour of dialysis, start the Study Drug infusion
- Obtain vital signs within 15 minutes prior to start of the Study Drug infusion, 15 ± 10 and 45 ± 10 minutes following the start of the Study Drug infusion and 0-15 minutes, 30-45 minutes, and 60-75 minutes following the end of the Study Drug infusion.
- Within 10 minutes after completing the Study Drug infusion, obtain blood samples
- Whenever feasible (e.g., first shift patients), obtain PK/PD blood samples 4 [+ 2] hours after completing the Study Drug infusion
- Record adverse events and any medication changes

5.4.2 *Week 1, Days 3 and 5*

- Obtain Central Laboratory blood samples within 15 minutes prior to the start of dialysis
- Obtain Central Laboratory blood samples within 10 minutes after the end of dialysis
- Record adverse event and any medication changes

5.4.3 *Week 2*

- Obtain Central Laboratory blood samples within 15 minutes prior to the start of dialysis
- Obtain a Local Laboratory (or point of care) INR (only for patients on warfarin)
- Obtain vital signs within 15 minutes prior to the start of dialysis
- Obtain Central Laboratory blood samples within 10 minutes after the end of dialysis
- Record adverse event and any medication changes

5.4.4 *Week 3*

- Prepare the Study Drug prior to the anticipated time of administration (see [Section 6.1.1](#) and Pharmacy Manual)
- Obtain Central Laboratory blood samples within 15 minutes prior to the start of dialysis
- Obtain a Local Laboratory (or point of care) INR (only for patients on warfarin)
- Any time prior to the last one hour of dialysis, start the Study Drug infusion
- Within 10 minutes after completing the Study Drug infusion, obtain blood samples
- Obtain vital signs within 15 minutes prior to the start of the Study Drug infusion and 15 ± 10 and 45 ± 10 minutes following the start of the Study Drug infusion and 0-15 minutes and 30-45 minutes following the end of the Study Drug infusion
- Record adverse events and any medication changes

5.4.5 *Week 4*

- Obtain Central Laboratory blood samples within 15 minutes prior to the start of dialysis
- Obtain a Local Laboratory (or point of care) INR (only for patients on warfarin)
- Obtain vital signs within 15 minutes prior to the start of dialysis
- Record adverse event and any medication changes

5.4.6 *Week 5*

- Prepare the Study Drug prior to the anticipated time of administration (see [Section 6.1.1](#) and Pharmacy Manual and Pharmacy Manual)
- Obtain Central Laboratory blood samples within 15 minutes prior to the start of dialysis
- Obtain a Local Laboratory (or point of care) INR (only for patients on warfarin)
- Any time prior to the last one hour of dialysis, start the Study Drug infusion
- Obtain vital signs within 15 minutes prior to the start of the Study Drug infusion and 15±10 and 45±10 minutes following the start of the Study Drug infusion and 0-15 minutes and 30-45 minutes following the end of the Study Drug infusion
- Record adverse events and any medication changes

5.4.7 *Week 6*

- Perform the hand grip strength prior to the start of dialysis (see instructions in the Study Reference Manual)
- Obtain Central Laboratory blood samples within 15 minutes prior to the start of dialysis
- Obtain a Local Laboratory (or point of care) INR (only for patients on warfarin)
- Obtain an ECG prior to the start of dialysis (see [Section 11.4.5.4](#))
- Have patient complete the FACIT-F questionnaire (see instructions in Study Reference Manual) prior to dialysis or during the first hour of dialysis
- Obtain vital signs within 15 minutes prior to the start of dialysis
- Perform a limited physical examination (see [Section 11.4.5.5](#))
- Record adverse events and any medication changes
- If not previously done, Schedule Cardiac MRI to occur on Week 12 [+ 2 weeks].

5.4.8 *Week 7*

- Prepare the Study Drug prior to the anticipated time of administration (see [Section 6.1.1](#) and Pharmacy Manual)
- Obtain Central Laboratory blood samples within 15 minutes prior to the start of dialysis
- Obtain a Local Laboratory (or point of care) INR (only for patients on warfarin)
- Any time prior to the last one hour of dialysis, start the Study Drug infusion

- Obtain vital signs within 15 minutes prior to the start of the Study Drug infusion and 15±10 and 45±10 minutes following the start of the Study Drug infusion and 0-15 minutes and 30-45 minutes following the end of the Study Drug infusion
- Record adverse events and any medication changes

5.4.9 *Week 8*

- Obtain Central Laboratory blood samples within 15 minutes prior to the start of dialysis
- Obtain a Local Laboratory (or point of care) INR (only for patients on warfarin)
- Obtain vital signs within 15 minutes prior to the start of dialysis
- Obtain Central Laboratory blood samples within 10 minutes after the end of dialysis
- Record adverse event and any medication changes

5.4.10 *Week 9*

- Prepare the Study Drug prior to the anticipated time of administration (see [Section 6.1.1](#) and Pharmacy Manual)
- Obtain Central Laboratory blood samples within 15 minutes prior to the start of dialysis
- Obtain a Local Laboratory (or point of care) INR (only for patients on warfarin)
- Any time prior to the last one hour of dialysis, start the Study Drug infusion
- Obtain vital signs within 15 minutes prior to the start of the Study Drug infusion and 15±10 and 45±10 minutes following the start of the Study Drug infusion and 0-15 minutes and 30-45 minutes following the end of the Study Drug infusion
- Record adverse events and any medication changes

5.4.11 *Week 10*

- Obtain Central Laboratory blood samples within 15 minutes prior to the start of dialysis
- Obtain a Local Laboratory (or point of care) INR (only for patients on warfarin)
- Obtain vital signs within 15 minutes prior to the start of dialysis
- Record adverse event and any medication changes

5.4.12 ***Week 11, Day 71***

- Prepare the Study Drug prior to the anticipated time of administration (see [Section 6.1.1](#) and Pharmacy Manual)
- Obtain Central Laboratory blood samples within 15 minutes prior to the start of dialysis
- Obtain a Local Laboratory (or point of care) INR (only for patients on warfarin)
- Obtain weight within 30 minutes prior to the start of the dialysis
- Obtain vital signs within 30 minutes prior to the start of dialysis
- Any time prior to the last one hour of dialysis, start the Study Drug infusion
- Obtain vital signs within 15 minutes prior to the infusion, 15 ± 10 and 45 ± 10 minutes following the start of the Study Drug infusion and 0-15 minutes and 30-45 minutes following the end of the Study Drug infusion.
- Obtain blood samples within 10 minutes after completing infusion
- Obtain blood samples within 10 minutes after completing dialysis
- Obtain vital signs within 30 minutes after dialysis
- Obtain weight post-dialysis within 30 minutes after completing dialysis
- Whenever feasible (e.g., first shift patients), obtain PK blood samples 4 [+2] hours after completing the Study Drug infusion
- Record net ultrafiltration for the dialysis session
- Record adverse events and any medication changes

5.4.13 ***Week 11, Day 75***

- Obtain Central Laboratory blood samples within 15 minutes prior to the start of dialysis
- Obtain a Local Laboratory (or point of care) INR (only for patients on warfarin)
- Obtain weight within 30 minutes prior to the start of the dialysis
- Obtain vital signs within 30 minutes prior to starting dialysis
- Obtain blood samples within 10 minutes after completing dialysis
- Obtain vital signs within 30 minutes after dialysis
- Obtain weight post-dialysis within 30 minutes after completing dialysis
- Record net ultrafiltration for the dialysis session
- Record adverse events and any medication changes

5.4.14 *Week 12/ET-1*

- Perform the hand grip strength prior to the start of dialysis (see instructions in the Study Reference Manual)
- Obtain Central Laboratory blood samples within 15 minutes prior to the start of dialysis
- Obtain a Local Laboratory (or point of care) INR (only for patients on warfarin)
- Obtain a weight within 30 minutes prior to the start of dialysis
- Obtain vital signs within 30 minutes prior to the start of dialysis
- Obtain an ECG prior to the start of dialysis (see [Section 11.4.5.4](#))
- Have patient complete the FACIT-F questionnaire (see instructions in Study Reference Manual) prior to dialysis or during the first hour of dialysis
- Obtain blood samples within 10 minutes after completing dialysis
- Obtain vital signs within 30 minutes after dialysis
- Obtain weight post-dialysis within 30 minutes after completing dialysis
- Record net ultrafiltration for the dialysis session
- Perform a limited physical examination (see [Section 11.4.5.5](#))
- Record adverse events and any medication changes
- Obtain a non-contrast cardiac MRI (see MRI Technical Manual for instructions)

5.5 **Safety Follow-Up Period Procedures (Study Weeks 13 – 24)**

5.5.1 *Weeks 14, 16, and 20*

- Obtain Central Laboratory blood samples within 15 minutes prior to the start of dialysis
- Obtain a Local Laboratory (or point of care) INR (only for patients on warfarin)
- Obtain vital signs within 30 minutes prior to the start of dialysis
- Record adverse events and any medication changes

5.5.2 *Weeks 18 and 24/ET-2*

- Obtain Central Laboratory blood samples within 15 minutes prior to the start of dialysis
- Obtain a Local Laboratory (or point of care) INR (only for patients on warfarin)

- Obtain an ECG prior to the start of dialysis (see [Section 11.4.5.4](#))
- Obtain vital signs within 30 minutes prior to the start of dialysis
- Perform a limited physical examination (see [Section 11.4.5.5](#))
- Record adverse events and any medication changes

5.6 Extended Follow-Up Procedures (Study Week 35)

5.6.1 Week 35

- Obtain Central Laboratory blood samples within 15 minutes prior to the start of dialysis

5.7 Unscheduled Visit

Additional clinical visits may be scheduled at the Investigators' discretion in order to follow or evaluate AEs. The reason for a given unscheduled visit will be recorded.

The following must be performed at any unscheduled visit occurring prior to Week 24:

- Record adverse events and any medication changes

5.8 Early Termination Visit

There are two possible types of Early Termination visits:

Early Termination Visit 1 (ET-1): Randomized patients terminating from the study prematurely prior to Study Week 12 should undergo an Early Termination Visit during which Week 12 procedures are performed. Patients terminating the study prior to Week 4 should not undergo the Week 12 cardiac MRI.

Early Termination Visit 2 (ET-2): Randomized patients terminating from the study prematurely after Study Week 12 visit, but before Week 24 should undergo an early termination visit during which Week 24 procedures are performed.

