4.3 Criteria for Discontinuation of Study Drug

Study Drug may be prematurely discontinued for a number of reasons, including:

- An intercurrent illness
- Any intolerable AE that cannot be ameliorated by appropriate medical intervention or that in the opinion of the Medical Monitor or Investigator would lead to undue risk if the patient were to continue on treatment

- Implementation of stopping rules (see [Section 4.4](#))
- Pregnancy
- Organ transplantation or development of another indication for chronic immunosuppression,
- Withdrawal of consent. A patient may elect to withdraw consent to treatment at any time.
 - Patients discontinuing Study Drug treatment after receiving any amount of Study Drug should undergo all follow-up study procedures unless the patient also explicitly withdraws consent for these procedures. The Study Drug has a long pharmacodynamic effect; therefore, continued monitoring for pharmacodynamic effects and safety is prudent. Patients withdrawing their consent for all study procedures must be given the option to continue to give consent for passive follow-up (i.e., by means of chart review) for adverse events through Study Week 24.

Reasons for all withdrawals/discontinuations of Study Drug will be recorded, and the Medical Monitor should be informed of all such cases as they occur.

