8.2 Infusion-Related Reactions, Hypersensitivity, and Anaphylaxis

Signs of a possible infusion-related reactions include fever, chills, pruritus, urticaria. Cardiopulmonary reactions including, but not limited to, chest pain, dyspnea, hypotension or hypertension may also be indicative of an infusion reaction, but some, such as hypotension may be difficult to distinguish from symptoms related to the dialysis procedure-related signs and symptoms. In these situations, Investigators must determine whether or not the symptom(s) represent an infusion-related reaction (e.g., by considering symptoms and symptom severity are typical for that patient, etc.).

Anaphylaxis is a severe, potentially fatal, systemic allergic reaction that occurs suddenly after contact with an allergy-causing substance, such as an investigational product.

For the purposes of this study, a hypersensitivity reaction is defined as an acute onset of an illness with involvement of the skin, mucosal tissue, or both during infusion of the Study Drug (but does not meet the definition of anaphylaxis described above).

If signs and symptoms of infusion-related reactions are observed during the infusion and the patient's cardiovascular status is stable:

- Reduce the flow rate of the infusion by at least half, and increase the infusion time.
- If the patient continues to show signs and symptoms of hypersensitivity, administer an IV dose of antihistamine, if the Investigator believes this is appropriate. The infusion may also be interrupted, if needed, and restarted at a flow rate that is at least 50% reduced.
- In patients who have experienced mild or moderate infusion reactions during prior Study Drug administrations, antihistamines and/or acetaminophen may be administered prophylactically prior to subsequent infusions, at the discretion of the Investigator.

In patients who experience severe (i.e., \geq Grade 3): infusion-related reactions, cardiopulmonary infusion reactions, anaphylaxis, or hypersensitivity (see definition and grading below):

- Permanently discontinue the Study Drug
- Treat the patients as for an anaphylactic reaction with IV antihistamines, corticosteroids, epinephrine, inhaled bronchodilators, and other measures as necessary

- Obtain a blood sample for the presence of anti-drug antibodies
- The patient should remain in the study for continued follow-up, but should receive no further Study Drug

CTCAE Grading for Infusion-Related Reactions

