11.4.5.6 Antibodies to COR-001

The immunogenic potential of COR-001 will be assessed by summarizing the number and percentage of patients who develop detectable anti-drug antibodies (ADA). Anti-drug antibody titers will be summarized descriptively for ADA positive samples and the impact of ADA on PK will be assessed if data allows. Neutralizing capacity of any detected ADA will be summarized.

11.4.6 *Pharmacokinetic Analysis and Pharmacokinetic/Pharmacodynamic Analysis*

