Study Week(s)	7	8	9	10	11		12/ET-1
Visit Window	±2 ¹⁴	±2	±2 ¹⁴	±2	±2 ¹⁴		±2
Study Day(s)	43	50	57	64	71	75	78
ESA and iron dosing per Appendix C							
Study Drug Administration [1]	X		X		X		
Lab Panel 1 [CHEM]							X [a]
Albumin				X			
Lab Panel 2 [LIP], Lp(a),							X [a]
Lab Panel 3 [INFL1]	X [a]		X [a]	X [a]	X [a]		X [a]
hsCRP	X [a]	X [d]	X [a]	X [a]	X [a,b,c]	X [a,d]	X [a]
Pre-Albumin	X [a]	X [d]	X [a]		X [a,b,c]	X [a,d]	X [a]
Lab Panel 4 [SPRBC]	X [a]	X [a]	X [a]	X [a]	X [a]		X [a]
Lab Panel 5 [HEME]	X [a]	X [a]	X [a]	X [a]	X [a]		X [a]
Lab Panel 6 [IRON]	X [a]	X [a]	X [a]	X [a]	X [a]		X [a]
Lab Panel 7 [PK]	X [a]	X [d]	X [a]		X [a,b,c]	X [a,d]	
Lab Panel 8 [CARD]					X [a,d]	X [a,d]	X [a,d]
Lab Panel 10 [ADA]	X [a]		X [a]		X [a]		
Lab Panel 11 [INFL2]	X [a]	X [d]	X [a]		X [a,b,c]	X [a,d]	X [a]
Lab Panel 12 [BIO]							X [a]
Serum pregnancy [2]							X [a]
Local Lab INR [3]	X [a]	X [a]	X [a]	X [a]	X [a]		X [a]
12-lead ECG pre-dialysis							X
FACIT-F [13]							X
Limited Physical Examination [5]							X
Vital Signs	X[7]	X[6]	X[7]	X[6]	X[7, 12]	X[12]	X[12]
Weight (pre-dialysis)					X[4]	X[4]	X[4]
Weight (post-dialysis)					X[8]	X[8]	X[8]
Record net ultrafiltration during dialysis					X[9]	X[9]	X[9]
Cardiac MRI							X[10]
Hand grip strength							X [11]
Adverse Events	X						
Concomitant Medications	X						

Laboratory test panels are defined in [Appendix D](#)

Every effort should be made to conduct the weekly study visits on the same day of the week (e.g. on Wednesdays)

ET-1 = Early Termination Visit 1 (see [Section 5.8](#))

[a], [b], [c], [d] Please see [Footnote i](#)

[1] The Study Drug is to be administered during dialysis over approximately 1 hour, starting any time prior to the last 1 hour of dialysis (see [Section 6.1.1](#))

- Study Visits during which Study Drug infusions are required should be planned on the same day of the week so that Study Drug administration can occur on a schedule of every 14 days.

- Whenever possible, keep the timing of the start of study drug relative to the start of dialysis constant (e.g., study drug is always started ~15 minutes after dialysis is started)
- Patients who miss a dose of Study Drug (e.g., due to a missed dialysis visit) may receive the missed Study Drug up to 96 hours (or 4 days) later. If the missed dose cannot be administered within this time frame, the dose should be considered “missed” and the next dose administered at the next study visit as planned.

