Appendix D Laboratory Measurements

Laboratory	Panel Name	Tests Included
Central	Panel 1: Chemistry [CHEM]	Sodium, potassium, chloride, bicarbonate (or CO ₂), calcium, phosphate, alanine aminotransferase (ALT), aspartate aminotransferase (AST), blood urea nitrogen (BUN) creatinine, total bilirubin, direct bilirubin, alkaline phosphatase, albumin, glucose
Central	Panel 2: Lipids [LIP]	Total cholesterol, low density lipoprotein (LDL) cholesterol, high density lipoprotein (HDL), triglycerides
Central	Panel 3: Inflammation 1 [INFL1]	serum amyloid A, hepcidin
Central	Panel 4: Special RBC Indices [SPRBC]	reticulocyte hemoglobin concentration (CHr), % hypochromic red cells (%HRC)
Central	Panel 5: Hematology [HEME]	Hemoglobin, hematocrit, reticulocyte count, red blood count (RBC) indices (e.g., mean corpuscular volume (MCV), red cell distribution width (RDW), platelets, white blood count (WBC), WBC differential
Central	Panel 6: Iron Indices [IRON]	TSAT, ferritin, iron, total iron binding capacity (TIBC)
Central	Panel 7: PK [PK]	COR-001
Central	Panel 8: Cardiac Markers [CARD]	Troponin T, NT-proBNP
Central	Panel 9: Infection Screen [INFEC]	HIV 1 and 2, Hepatitis B surface antigen, Hepatitis B surface antibody, Hepatitis C antibody, mycobacterium tuberculosis blood test (i.e., interferon gamma release assay)
Central	Panel 10: Anti-Drug Antibodies [ADA]	Anti-COR-001 binding antibodies and neutralizing antibodies (if binding antibodies are detected)
Central	Panel 11: Inflammation 2 [INFL2]	Total and free IL-6
Central	Panel 12: Future biomarkers [BIO]	Future cardiac, renal, and hematologic markers, including gene variations, ribonucleic acid, or protein markers
Central	Panel 13: B-Vitamins [BVIT]	B-12, folate
Central	Other individual tests	Screening (total) IL-6, genotype, intact parathyroid hormone [PTH], lipoprotein a [Lp(a)], pregnancy [β -hCG in women of childbearing potential only], follicle-stimulating hormone (FSH), stool occult blood, pre-albumin, hsCRP
Local	Coagulation	International normalized ratio (INR) (warfarin-treated patients only)

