8.9 ANTIBODIES TO COR-001

The immunogenic potential of COR-001 will be assessed by summarizing the number and percentage of patients who develop detectable anti-drug antibodies (ADA) by dose. Anti-drug antibody titers will be summarized descriptively for ADA positive samples and the impact of ADA on PK will be assessed if data allows. Neutralizing capacity of any detected ADA will be summarized.

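### The early-termination visit before Week 12 (ET-1) has no anti-drug-antibody or drug-level sample, so a patient dosed on schedule who leaves the study there has no scheduled antibody test after the last dose

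*Protocol*

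**What the plan says.** Protocol 5.8 defines two exit visits. Patients leaving the study "prior to Study Week 12 should undergo an Early Termination Visit during which Week 12 procedures are performed" (ET-1). Those leaving after the Week 12 visit but before Week 24 have the Week 24 procedures instead (ET-2).

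Protocol 5.4.14 (Week 12/ET-1) names no ADA or PK sample. It gives only the general instruction "Obtain Central Laboratory blood samples within 15 minutes prior to the start of dialysis", in the same words as for Day 1 in 5.4.1, and the list of tests is left to Appendix A. There:

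- The row beginning "Lab Panel 10 [ADA" is marked, always pre-dialysis, at Days 1, 15, 29, 43, 57 and 71, all of them dosing days. After that it is marked at Week 24/ET-2 (Day 162) and Week 35 (Day 239).
- The Panel 7 (PK) row is marked at Days 1, 3, 5, 8, 15, 29, 43, 50, 57, 71 and 75, then at Weeks 14, 18 and 35.
- The 12/ET-1 cell is empty in both rows. The 24/ET-2 cell is empty for PK only.

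Appendix D places the antibody tests in Panel 10 and the COR-001 level in Panel 7, so no other panel supplies them.

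Two other provisions bear on the point. For severe (Grade 3 or higher) reactions, Protocol 8.2 adds "Obtain a blood sample for the presence of anti-drug antibodies". Protocol 4.3 says "Patients discontinuing Study Drug treatment after receiving any amount of Study Drug should undergo all follow-up study procedures", unless the patient explicitly withdraws consent for those procedures.

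For the analysis, SAP 8.9 plans on "summarizing the number and percentage of patients who develop detectable anti-drug antibodies (ADA) by dose". Neither it nor Protocol 11.4.5.6 states a denominator.

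**The concern.** Immunogenicity is a named secondary objective (Protocol 2), ADA belongs to a secondary safety endpoint (3.1.2), and the effect of ADA on PK is to be examined if the data allow (11.4.5.6, SAP 8.9). Protocol 3.5.2 justifies antibody testing out to Week 35 by the slow clearance of the drug. A patient who leaves at ET-1 loses the Week 24 and Week 35 samples, so the exit visit is the last opportunity to look for antibodies. Blood is drawn at that visit, but not for this purpose.

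The two exit visits also treat similar patients differently. Someone who leaves just after the Week 12 visit goes to ET-2 and has an ADA sample. Someone who leaves just before it goes to ET-1 and has none. The documents give no reason for the difference, which looks like a by-product of reusing the Week 12 column.

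For PK, both exit columns include total and free IL-6 (Panel 11) without a drug level, although relating drug level to IL-6 is a secondary objective.

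**Working it through.** The plan states no figure on this point, so there is none to reproduce. The check is a reading of the schedule followed by simple arithmetic.

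**1. Gap between the last scheduled sample and an ET-1 exit.** For each exit day d from 2 to 77, gap = d minus the latest scheduled sample day not after d. Days are nominal.

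- ADA (Days 1, 15, 29, 43, 57, 71): the maximum is 13 days (exit on Day 14, 28, 42, 56 or 70; for example 28 − 15 = 13). The gaps sum to 476 over 76 exit days, so the mean is 476/76 = 6.3 days.
- PK (Days 1, 3, 5, 8, 15, 29, 43, 50, 57, 71, 75): the maximum is 13 days (exit on Day 28, 42 or 70). The mean is 350/76 = 4.6 days.

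Visit windows (±2 days, or +4 for a late dose) and missed visits widen these gaps. With a sample at ET-1, both become 0.

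**2. What the ADA gap covers.** Each sample before Week 12 precedes that day's infusion. For a patient dosed on schedule, the gap is therefore the whole interval from the last dose to exit. A patient leaving before Day 15 has only the Day 1 pre-dose sample, because Days 3, 5 and 8 carry PK but not ADA.

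**3. Comparison with completers.** A completer also has a long unsampled stretch (162 − 71 = 91 days), but then has two ADA samples after the last dose, on Days 162 and 239.

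**4. ET-2.** ADA is drawn at the visit, so its gap is 0. The last PK sample is on Day 120 (Week 18), so for an exit on Day 161 the nominal PK gap is 161 − 120 = 41 days.

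**5. Effect on the ADA percentage, illustration only.** Suppose all ET-1 leavers stay in the denominator, all ADA in them is missed, and leaving is unrelated to ADA. Then observed rate = p × (1 − d), where p is the true ADA rate and d the share leaving at ET-1. Both are assumed.

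| True rate p | d = 5% | d = 10% | d = 20% |
|---|---|---|---|
| 5% | 4.8% | 4.5% | 4.0% |
| 10% | 9.5% | 9.0% | 8.0% |
| 20% | 19% | 18% | 16% |

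With 6 cohorts × 8 = 48 active patients, these values of d mean 2.4, 4.8 and 9.6 leavers. If leavers are instead excluded as missing, this dilution does not arise, again provided that leaving is unrelated to ADA.

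**6. Granularity.** One cohort gives 8 active patients at a dose and two cohorts give 16. One missed positive is 1/8 = 12.5 or 1/16 = 6.25 percentage points. This is the weight of a single patient, not an estimate of bias.

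**The case against.** The strongest reply is that few patients are affected and that those of most concern are already covered. Patients who stop drug are kept on the full schedule by Protocol 4.3, including Weeks 24 and 35. Severe reactions trigger their own ADA sample under 8.2, and those patients stay in follow-up. ET-1 applies only to patients leaving the study. The reasons listed in 5.8.1, which are given as examples, are withdrawal of consent for all procedures and discontinuation of the study by the sponsor. A patient who refuses all procedures may give no exit sample whatever Appendix A says. Earlier ADA samples remain available, and PK modelling is specified in a separate plan.

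Most of this stands, and it limits the size of the point. It does not close the gap. The 8.2 sample is not triggered by milder reactions, other adverse events or leaving by choice, and 4.3 protects only those who stay. Unscheduled visits (5.7) require no blood sample.

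A reader might go further and infer that leavers are in effect counted as ADA-negative, so that reported incidence is biased downwards. The documents do not say this. Protocol 11.3.4 leaves missing data unimputed and excludes them. SAP 2.4 allows a separate missing category, with missing values in the denominator where appropriate. SAP 8.4 bases percentages for qualitative Appendix D parameters on non-missing results. What remains is narrower: a leaver whose earlier post-dose samples were negative has non-missing results and could be tabulated as not having developed ADA.

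A reader might also infer that every early leaver lacks an exit ADA sample. That is wrong for ET-2, which includes one.

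**Conclusion.** The schedule gap is real and follows directly from Protocol 5.8 and Appendix A: ET-1 has neither ADA nor PK, and ET-2 has ADA without PK. It affects only patients who leave the study. For ET-1 leavers dosed on schedule, no planned ADA sample follows the last dose; for those leaving before Day 15, no planned ADA sample follows any dose.

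The point is minor. The nominal gap is at most 13 days, before visit windows and missed visits. The effect on the ADA percentage cannot be computed, since no dropout or ADA rate is given and the ADA sections do not define the denominator. Under the assumed rates and the worst-case handling shown above, a true 10% would read as 8.0% to 9.5%. The change is worth making because it is cheap and a sample not taken at exit cannot be recovered.

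**What to change.** In Protocol Appendix A, add Panel 10 [ADA] and Panel 7 [PK] to the 12/ET-1 column with a footnote limiting them to ET-1, and add Panel 7 to the 24/ET-2 column with a footnote limiting it to ET-2. Take them from the pre-dialysis draw already made at those visits.

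As a secondary clarification, state in SAP 8.9 that the ADA percentage is based on patients with at least one post-dose ADA result, and report by dose the number without one. This settles how patients leaving before Day 15 are handled. It does not help a later leaver with earlier negative results; for that patient the exit sample is what adds information.

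The cost is one or two extra tubes and the assays in the few patients who terminate early, plus amendment and SAP wording. An exit sample does not replace the lost Week 24 and Week 35 samples, and it cannot be obtained from patients who refuse all procedures or have already left.
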